1. Statistically significant abdominal fat reduction post UltraShape Power treatments as measured by Ultrasound device at Pre Tx.3, 4 weeks, and 8 weeks follow-up (4wk FU and 8wk FU) versus baseline.
2. Statistically significant abdominal fat reduction post UltraShape Power treatments as measured by calibrated Caliper at Pre Tx.2, Pre Tx.3, 4 weeks, 8 weeks and 12 weeks follow-up (4wk FU, 8wk FU and 12wk FU) versus baseline.
3. Statistically significant abdominal circumference reduction post UltraShape Power treatment/s at Pre Tx.2, Pre Tx.3, 4 weeks, 8 weeks and 12 weeks follow-up (4wk FU, 8wk FU and 12wk FU) versus baseline.
4. Investigator satisfaction:
Satisfaction assessment will be performed by the study investigator using a pre-defined scale questionnaire. The investigator will answer this questionnaire at each follow-up visit (4wk FU, 8wk FU and 12wk FU).
5. Subject improvement and satisfaction:
Improvement and satisfaction assessment will be performed independently by the subject himself using a pre-defined scale questionnaire. The subjects will answer this questionnaire at each follow-up visit (4wk FU, 8wk FU and 12wk FU).

Primary and Secondary Efficacy Endpoint

Primary and secondary objectives will be measured using the next efficacy endpoints:

1. Fat thickness measurements using Ultrasound device
2. Fat thickness measurements using calibrated Caliper
3. Circumference measurements of the abdominal area using Measuring Tape
4. Investigator satisfaction using a pre-defined scale
5. Subject improvement and satisfaction using a pre-defined scale
6. Photography

 Syneron Medical Ltd. Confidential	Clinical Study to Evaluate the Safety and Efficacy of the UltraShape Power Device Using the U-Sculpt Power Transducer for Abdominal Fat and Circumference Reduction			
	Protocol #	DHF21621	Rev. Date	April 05, 2016

Primary Safety Endpoint

The number, severity and type of any adverse event recorded throughout the study and post treatment (discomfort (pain), immediate and delayed response).

1. Occurrence of expected post treatment immediate response including erythema and edema and during all study period based on predefined scale (Table 4).
2. Number, severity and type of any adverse event recorded throughout the course of the study.

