Perform the UltraShape Power utilizing the U-Sculpt Power Transducer treatment according to the instruction in the User Manual.

Expected post treatment side effects are limited to Erythema (blanchable/non-blanchable), Edema, Heat sensation and pain sensation.

Post Treatment Procedures

1. Pain assessment – immediately after each treatment the subjects will be asked to rank the pain sensation during treatment using Numerical Scale Response (NSR; see Appendix III) for the UltraShape Power procedure
2. Safety aspect will be assessed before and after each treatment:
 - a. Clinical effects - All visible and palpable immediate response will be recorded for the entire treatment area using a 4-point severity scale (Table 4)
 - b. Adverse Events – Record the number, severity and type of any adverse event occurred before, through and after treatments.

Return Visits

All subjects will be requested to return to the clinic at the following time-points during the study in order to assess the clinical performance of the device:

- Visit 4: FU1 – 4 weeks (± 7 days) post last treatment.
- Visit 5: FU2 – 8 weeks (± 7 days) post last treatment.
- Visit 6: FU3 – 12 weeks (± 7 days) post last treatment.

At each return visit the following procedures will be conducted and data recorded:

- Weight.
- Ultrasound fat-thickness measurements.
- Caliper fat-thickness measurements.
- Circumference measurements.

SYNERON CANDELA Syneron Medical Ltd. Confidential	Clinical Study to Evaluate the Safety and Efficacy of the UltraShape Power Device Using the U-Sculpt Power Transducer for Abdominal Fat and Circumference Reduction			
	Protocol #	DHF21621	Rev. Date	April 05, 2016

- Skin assessment for clinical effects due the procedures:
 - Post treatment response and adverse events.
- Photographs as conducted at baseline.
- Satisfaction questionnaire performed by the investigator using the Global Aesthetic Improvement (GAI).
- Completion of the Subject Follow Up questionnaire:
 - Subjective Improvement and satisfaction performed by the subject using the Global Aesthetic Improvement (GAI).
- At the final visit a urine pregnancy test will be performed for women with bearing potential.

DATA ANALYSIS

Recording

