An adverse event (AE) is any adverse change in health or side effect that occurs in a study participant during their participation in the study.

Anticipated Adverse Effects

Following treatment with the UltraShape Power the following local adverse effects could occur (anticipated):

- Purpura
- Blister
- Bruising
- Bullae
- Erosion
- soreness
- First degree burn
- Second degree burn

An adverse event (AE) is any undesired clinical occurrence in a study subject as indicated by signs, symptoms, illnesses, events that develop or worsen in severity in association with the study when deemed by the Investigator to be related to use of the device or study procedures. The Investigator will document all adverse signs and symptoms regardless of severity or frequency that are either volunteered by subjects or observed during the course of the study that are related to the device. The Investigator will also record adverse experiences of subjects resulting from concurrent illnesses, reactions to concurrent medications, or progression of disease states that the Investigator deems related to the device. Included in the description will be the nature of the sign or symptom, the date of onset, whether the event was serious, the severity, the relationship to study procedures or investigational device, the action taken, the

 Syneron Medical Ltd. Confidential	Clinical Study to Evaluate the Safety and Efficacy of the UltraShape Power Device Using the U-Sculpt Power Transducer for Abdominal Fat and Circumference Reduction			
	Protocol #	DHF21621	Rev. Date	April 05, 2016

date of resolution, and the outcome. The Principal Investigator will determine the relationship of the adverse device effect to the investigational device.

Unanticipated Adverse Device Effects

For device studies, part 21 CFR 812.3(s) uses the term unanticipated adverse device effect which is defined as any serious adverse effect on health or safety or any life-threatening problem or death caused by, or associated with the device, if that effect, problem, or death was not previously identified in nature, severity, or degree of incidence in the investigational plan or application (including a supplementary plan or application), or any other unanticipated serious problem associated with a device that relates to the rights, safety, or welfare of subjects.

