Significant device failure may constitute an adverse event if an undesirable experience occurs. This definition includes any event resulting from insufficiencies or inadequacies in the instructions for use or the deployment of the device, or any event that is a result of a user error.

All unanticipated adverse effects will be graded as follows:

Mild: Sign or symptom, usually transient, non-life-threatening requiring no special treatment and generally not interfering with usual activities.

Moderate: Sign or symptom, non-life-threatening which may be ameliorated by simple therapeutic measures, and may interfere with usual activity.

Major: Sign or symptom that is intense or debilitating but non-life-threatening and that interferes with usual activities. Recovery is usually aided by therapeutic measures and the discontinuation of the study device may be required.

Severe: Any untoward medical occurrence that at any time results in death or life-threatening illness, resulting in persistent or significant disability/incapacity.

The relationship of the adverse effect to the study is defined as follows:

Probable: An adverse event has a strong temporal relationship to study device, and another etiology is unlikely or significantly less likely.

Possible: An adverse event has a strong temporal relationship to the study device, and an alternative etiology is equally or less likely compared to the potential relationship to study device.

Probably not: An adverse event has little or no temporal relationship to the study device and/or a more likely alternative etiology exists.

Not related: An adverse event has no temporal relationship to study device or has a much more likely alternative etiology.

 Syneron Medical Ltd. Confidential	Clinical Study to Evaluate the Safety and Efficacy of the UltraShape Power Device Using the U-Sculpt Power Transducer for Abdominal Fat and Circumference Reduction			
	Protocol #	DHF21621	Rev. Date	April 05, 2016

Reporting Adverse Events (AE) and Serious Adverse Events (SAE)

Anticipated Adverse Events: Anticipated adverse events in this study include Purpura, blistering, bruising, bullae, erosion, soreness and burn. If an unanticipated adverse event occurs at any time during or after the use of the UltraShape Power device, the Investigator must report it to Syneron.

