Over 1000 subjects worldwide participated in clinical research and underwent treatment with the different *UltraShape* devices. The *UltraShape Power* device will be used in this study was previously used in studies and emitted the same acoustic energy. To date, no serious adverse events or unanticipated AEs have been reported. The reported AEs relate to skin and subcutaneous tissue, confined to the treatment area and were all mild in nature and resolved within the study period.

Potential benefits to participating individuals and to society

Subjects may or may not benefit from reduction of subcutaneous fatty tissue on the treated area via a non-invasive technique resulting in body contouring improvement. All subjects in the treatment groups are expected to have some benefit from the treatment procedures as would be expected for the commercial devices (*UltraShape Power*). Subject will receive all treatment procedures at no cost. This study will benefit the advancement of medicine by generating data on safety and efficacy that will aid in the development of an alternative treatment options to procedures with higher potential risks subjects, such as liposuction. The results of this study will help to determine whether this device is safe and effective for improvement of localized subcutaneous fat.

Conclusion:

In light of the potential benefits of non-invasive body contouring relative to its risks, the potential benefits associated with the use of the *UltraShape Power System* outweigh its risks, supporting study initiation.

ETHICS AND GOOD CLINICAL PRACTICE

This study will be carried out in compliance with the following:

- Syneron Standard Operating Procedures.
- Declaration of Helsinki, concerning medical research in humans (Recommendations Guiding Physicians in Biomedical Research Involving Human Subjects, Helsinki 1964, amended Tokyo, 1975, Venice 1983, and Hong Kong 1989).
- US Code of Federal Regulations (Title 21CFR including parts 50, 56 and 812 governing informed consent and IRB regulations).
- International Conference on Harmonization (ICH) Harmonized Tripartite Guideline for Good Clinical Practice (GCP), 1996.

 Syneron Medical Ltd. Confidential	Clinical Study to Evaluate the Safety and Efficacy of the UltraShape Power Device Using the U-Sculpt Power Transducer for Abdominal Fat and Circumference Reduction			
	Protocol #	DHF21621	Rev. Date	April 05, 2016

QUALITY ASSURANCE AND STUDY MONITORING

Study Monitoring/Auditing/Inspection

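### The grading scale for unanticipated adverse effects defines Severe by outcome rather than intensity, so an intense or debilitating but non-life-threatening event ranks below Severe and some events fit no grade.

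*Combined protocol and SAP*

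**What the plan says.** Severity is part of the safety endpoint. Primary Safety Endpoint, item 2, is: "Number, severity and type of any adverse event recorded throughout the course of the study". Item 1 of the same list covers expected immediate responses such as erythema and edema, graded on Table 4.

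Under Anticipated Adverse Effects, the description of each event must include "whether the event was serious, the severity, the relationship to study procedures or investigational device", so seriousness and severity are separate items.

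The grades come under Unanticipated Adverse Device Effects, with this lead-in: "All unanticipated adverse effects will be graded as follows". Mild, Moderate and Major are each a sign or symptom and each non-life-threatening. The upper two grades are:

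- "Major: Sign or symptom that is intense or debilitating but non-life-threatening and that interferes with usual activities"
- "Severe: Any untoward medical occurrence that at any time results in death or life-threatening illness, resulting in persistent or significant disability/incapacity"

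Table 4 (Appendix II) runs 0 absent, 1 mild, 2 moderate, 3 severe, and does not define the levels. Post Treatment Procedures applies it to all visible and palpable immediate responses.

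The section on reporting adverse events states: "Anticipated adverse events in this study include Purpura, blistering, bruising, bullae, erosion, soreness and burn". No graded definitions are attached to that list.

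**The concern.** A severity scale normally ranks how intense an event is, while seriousness describes its outcome. The first three grades here follow intensity, and the fourth switches to outcome. The scale therefore cannot describe a very intense event by its top label, and its top label repeats what the seriousness item already captures.

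At stake is how the primary safety endpoint reads. The Risks section already summarises past experience by severity label, describing earlier events as all mild. A reader of a similar sentence about severe events would take it to concern intensity, which this Severe grade does not measure. Up to ten sites will also grade from one ambiguous sentence, so the same event could receive different grades at different sites.

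**Working it through.** The plan states no adverse-event rate, safety threshold or safety sample-size calculation, so there is no figure to reproduce. The check is mainly one of reading.

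**Step 1: place event types on the scale.** The second column takes the Severe sentence literally, with lasting disability as a condition on the life-threatening illness. The third supposes that an *or* was lost before the disability clause.

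| Event | Literal reading | With an *or* restored |
|---|---|---|
| Intense or debilitating, not life-threatening, no lasting disability | Major | Major |
| Lasting disability, never life-threatening | Not Severe; Major at most | Severe, and also Major if debilitating |
| Life-threatening, full recovery | No grade, since the lower three exclude it and Severe needs disability | Severe |
| Life-threatening, lasting disability | Severe | Severe |

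The first row is the same under both readings. The second and third rows change with the reading. Restoring the *or* closes the gap in the third row but creates an overlap of Major and Severe in the second.

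**Step 2: compare with the other rules.** The event description asks for seriousness and severity separately, yet the top severity grade consists of seriousness criteria. Table 4's level 3 carries no threat-to-life condition. A strong immediate erythema can therefore be severe under item 1 of the endpoint, while an intense unanticipated reaction under item 2 cannot be if it does not threaten life.

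**Step 3: check the scope.** The lead-in limits the four grades to unanticipated effects. Blisters, bullae, erosion and burns are listed as anticipated, so unless they are immediate responses recorded on Table 4, the text assigns them no scale. Table 2 mentions an adverse events form with severity ratings. That form is not in the available text, so what it defines is unknown.

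**Step 4: how likely is a count of zero Severe?** Inputs: 120 subjects (Number of Subjects, stated as a maximum) and an assumed per-subject rate p of events that meet the Severe grade. P(0) = (1 − p)^120.

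| Assumed p | P(0 in 120) |
|---|---|
| 0.01% | 98.8% |
| 0.05% | 94.2% |
| 0.1% | 88.7% |
| 0.5% | 54.8% |
| 1% | 29.9% |

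P(0) reaches 95% only if p is at most 1 − 0.95^(1/120) = 0.043%. The Risks section says: "Over 1000 subjects worldwide participated in clinical research and underwent treatment with the different" UltraShape devices, with no serious events reported. Taking this as 0 of 1000, the one-sided 95% upper bound on p is 1 − 0.05^(1/1000) = 0.30%, at which P(0) = (1 − 0.0030)^120 = 69.8%.

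**The case against.** The strongest reply is that little of practical weight passes through this scale. It is stated for unanticipated effects only. The local reactions one would expect from this device are listed as anticipated, and the Risks section reports no unanticipated events to date. Table 4 lets a strong immediate reaction be recorded as severe. Major is a defined level and its events are still recorded. Seriousness is captured separately, and the missing *or* looks like a drafting slip.

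Most of this is correct and limits the point. The scope limit means that the scale cannot be treated as the grading of every adverse event, and no data are lost. What stands is that the first row of the table in Step 1 does not depend on any slip, that the sentence as written gives different grades under two plausible readings, and that Table 4 supplies a second meaning of Severe rather than a cure. The scope limit also exposes a further gap, because most anticipated events have no defined grade.

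A reader might go further and infer that the definition all but guarantees a finding of no severe events. The documents do not support that. It depends on an assumed rate, and at the upper bound from the plan's own history the chance of zero is about 70%. Table 4 can also produce severe entries.

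**Conclusion.** The point holds as a fault of definition. The four-grade scale mixes intensity with outcome, conflicts with the plan's own separation of seriousness from severity, and uses Severe differently from Table 4 within one primary safety endpoint. Read literally, it also leaves life-threatening events without lasting disability ungraded. It should be corrected, ideally before grading begins.

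The consequence is mislabelling and inconsistent grading in the safety summary. No success criterion rests on an absence of severe events, and the efficacy analysis is untouched. The size cannot be put as a rate, because the documents give no frequency for intense but non-life-threatening reactions.

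Two further inferences should be avoided. Comparing an upper limit for life-threatening events with a rate of intense reactions would set two different quantities against each other. Nor can it be said outright that disabling reactions rank below Severe: with the *or* restored, a lasting disability is Severe, and the plan's own word in the Major grade is debilitating.

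The conclusion assumes that the unseen adverse events form does not already define severity differently.

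**What to change.** - Use one intensity scale, Mild, Moderate and Severe, for all adverse events, anticipated and unanticipated. Let the present Major wording define Severe and drop Major as a separate level.
- Give Table 4's levels definitions that agree with that scale.
- Move death, life-threatening illness, and lasting or significant disability to the seriousness item, as alternatives joined by *or*.
- Tabulate severity and seriousness separately.

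If the scale cannot be replaced, the minimum is to repair the *or* and report Major and Severe together, with their definitions printed beside the table. Reporting them together also absorbs the overlap that the *or* creates.

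The cost is a wording change to the protocol and CRF, and a severity table that may look slightly less favourable.

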Assure repeatable marking of treatment area at each treatment visit

STUDY DESIGN OVERVIEW

This study is a prospective, baseline controlled, multi-center, one arm clinical study showing the performance and safety of the UltraShape Power treatment for abdominal non-invasive fat and circumference reduction.

Up to 120 Healthy subjects in up to 10 investigational sites will be enrolled in this study. All subjects will undergo an assessment of their general health. During the treatment period, subject’s fat thickness and circumference will be measured and three successive bi-weekly (two weeks interval) treatments will be performed.

The study subjects will undergo treatments with UltraShape Power device utilizing the U-Sculpt Power Transducer.

During the follow-up period visit will be conducted as follow: 4 weeks (4wk FU), 8 weeks (8wk FU) and 12 weeks (12wk FU) post last treatment (Tx.3). Subject’s fat thickness will be measured in two different methods (Caliper & Ultrasound) and fat reduction will be assessed at each post baseline visit. Circumference will be measured in 3 measurements heights and circumference reduction will be assessed at each post baseline visit. Additionally, investigator and subject questionnaires will be completed. Finally, photography will be performed under visible light conditions of the front, right, left and back view. Most of the assessments will occur at each of the visits to the clinic.

SUTDY OBJECTIVE

The objective of this trial is to evaluate the safety and efficacy of the UltraShape Power device utilizing the U-Sculpt Power Transducer for abdominal non-invasive fat and circumference reduction

Primary Objective

Statistically significant abdominal fat reduction as measured by Ultrasound device post UltraShape Power treatments at 12 weeks follow-up (12wk FU) versus baseline.

 Syneron Medical Ltd. Confidential	Clinical Study to Evaluate the Safety and Efficacy of the UltraShape Power Device Using the U-Sculpt Power Transducer for Abdominal Fat and Circumference Reduction			
	Protocol #	DHF21621	Rev. Date	April 05, 2016

Primary Safety Objective

1. Evaluate the safety of the treatment with the UltraShape Power device utilizing the U-Sculpt Power Transducer during all study.
2. Comfort level during treatment:
Comfort assessment will be performed independently by the subject himself using NSR scale; the subjects will answer this questionnaire after each treatment (Tx.1, Tx.2 and Tx.3).

Secondary Objectives

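### The relationship scale lets an undefined timing criterion alone give a negative rating, and one of the protocol's two adverse-event definitions may then leave a delayed effect unrecorded

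*Combined protocol and SAP*

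**What the plan says.** All of this is in the combined protocol and SAP.

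**The scale** (Adverse Events, under Unanticipated Adverse Device Effects) has four categories:

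- *Probable* sets a condition on timing and a condition on cause, and both must hold: "An adverse event has a strong temporal relationship to study device, and another etiology is unlikely or significantly less likely".
- *Possible* keeps the timing condition unchanged and relaxes only the one on cause: "An adverse event has a strong temporal relationship to the study device, and an alternative etiology is equally or less likely".
- *Probably not* can be reached through either of its two conditions: "An adverse event has little or no temporal relationship to the study device and/or a more likely alternative etiology exists".
- *Not related* has the same either-or structure, with both conditions made stricter: "An adverse event has no temporal relationship to study device or has a much more likely alternative etiology".

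No section defines a temporal relationship, says what makes it strong, or sets an onset window. The rating is left to one judge per site: "The Principal Investigator will determine the relationship of the adverse device effect to the investigational device".

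**The definitions of an adverse event.** The Adverse Events section opens with a broad definition: any unfavourable health change or side effect arising while the subject takes part. Under Anticipated Adverse Effects a second definition limits the term to events that the investigator considers related to the device or the study procedures. The duty to document signs and symptoms that follows it is limited in the same way.

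**The endpoint.** Primary Safety Endpoint reads "The number, severity and type of any adverse event recorded throughout the study and post treatment (discomfort (pain), immediate and delayed response"). The Safety Endpoints row of the synopsis (Table 1) also names delayed response, and neither place defines it. The Safety paragraph of Data Analysis has all complications recorded from the start of the study, without reference to relatedness. Return Visits schedules a skin assessment for procedure effects at 4, 8 and 12 weeks after the last treatment.

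**The concern.** The two halves of the scale are built differently. The positive categories join timing and cause with *and*, so both conditions must hold. The negative categories join them with *and/or* or *or*, so either is enough. Timing therefore acts as a veto: if it is not strong, the positive ratings are closed, whatever is known about other causes.

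That fits poorly with an endpoint that names delayed response. A delayed effect is the kind of event whose link in time to treatment is most open to argument, and the scale has no wording for an event that is late but plausibly caused by the device.

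Two things depend on it. One is the label: the same late event could be rated differently across up to ten sites, because each investigator must supply a meaning for the key term. The other is the record: under the second adverse-event definition, an event not considered related is not an adverse event at all. With one arm there is no control group in which an excess of late local events could show, so attribution rests on these ratings.

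**Working it through.** The plan gives no figure on this point, so the check is a reading of the definitions against each other.

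**Step 1: cross the two criteria.** Timing takes three levels in the definitions (strong, little, none). The alternative cause takes four (unlikely or significantly less likely; equally or less likely; more likely; much more likely). That gives 3 × 4 = 12 combinations. Each cell shows every category whose wording it meets.

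| Timing | Other cause unlikely | Equally or less likely | More likely | Much more likely |
|---|---|---|---|---|
| Strong | Probable, Possible | Possible | Probably not | Probably not, Not related |
| Little | Probably not | Probably not | Probably not | Probably not, Not related |
| None | Probably not, Not related | Probably not, Not related | Probably not, Not related | Probably not, Not related |

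**Step 2: count.**

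- Combinations with timing that is not strong: 2 × 4 = 8. Of these, 0 can be Probable or Possible.
- Combinations among those 8 with no more likely alternative cause: 2 × 2 = 4. Here timing alone decides the rating.
- In the two of these four with little temporal relationship, only Probably not fits. Not related on timing alone needs no temporal relationship at all, which is the other two.

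**Step 3: place a delayed event in the table.** Take a change in the treated area that begins weeks after the last treatment and has no other explanation. If the investigator reads temporal relationship as closeness in time, the event falls in the *Little* row and only Probably not fits. If the investigator reads it as a course in keeping with the treatment, the event can sit in the *Strong* row and be rated Possible or Probable. The protocol does not choose between these readings.

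**Step 4: follow the rating to the record.** Under the opening definition, the Primary Safety Endpoint and the Safety paragraph of Data Analysis, the event is recorded whatever its rating. Under the second definition and its documentation duty, it is recorded as an adverse event only if considered related. The protocol does not say which definition governs, or which of the four categories count as related. If Probably not is taken as not related, the second definition leaves the event out.

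**The case against.** The strongest reply is that the wording is loose but leaves the investigator free to reach a sensible rating. Several stronger readings are tempting, and the documents do not support them.

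- *A reader might infer that late-onset effects are downgraded by rule.* They are not. The criterion is the strength of a temporal relationship, and no latency limit is set. Rating a late event Possible need not depart from the written definition.
- *A reader might infer that late effects are classed as unrelated.* Weak timing gives Probably not, which is a separate grade from Not related.
- *A reader might infer that such events drop out of the safety endpoint.* The endpoint counts any adverse event, and Data Analysis records all complications; neither has a relatedness filter. Loss is a risk, through the second definition only.
- *A reader might infer a downward bias in a device-related event rate.* The documents define no such rate, so no bias in one can be shown.
- *A reader might use the follow-up share, 12 of 16 weeks or 75%, as the size of the problem.* That is calendar time. It measures neither events nor misclassification.
- *A reader might set the 12-week efficacy objective against this scale and see benefit credited late while harm is not.* The objective is a group comparison with baseline. It attributes nothing case by case, so there is no contradiction.

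The reply also notes that the date of onset must be recorded, so ratings can be re-examined, and that unanticipated adverse events must be reported at any time with no relationship threshold. Both are fair. But re-examination needs the event to have been recorded, and the reporting duty applies to adverse events, which leads back to the question of which definition governs.

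What stands of the reply is that harm is possible and not established. It does not answer the structure of the scale or the clash between the two definitions.

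**Conclusion.** The point holds in a limited form and is worth correcting. As written, timing alone can produce a negative rating with no alternative cause, and less than strong timing can never be rated Possible. That sits badly with a safety endpoint that includes delayed response.

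The effect on a given event rests on three assumptions: that the investigator reads the timing term as closeness to treatment; that Probably not is treated as not considered related; and, for loss of the record, that the site works from the second adverse-event definition. The documents neither require nor exclude any of these. They also give no expected number of late local events, so the size can be stated only as the structural count in the table.

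**What to change.** 1. **Relationship scale.** In Probable and Possible, replace the requirement for a strong temporal relationship with *plausible temporal relationship, including delayed onset*. In Probably not require a more likely alternative cause, and in Not related a much more likely one, so that timing alone does not suffice for either. The rating stays with the Principal Investigator; no automatic minimum rating for unexplained local signs is proposed, since that would override the investigator's judgement.
2. **Adverse-event definitions.** Reconcile the two so that every event is recorded regardless of its rated relationship, in line with the Primary Safety Endpoint and the Safety paragraph of Data Analysis. Changing the scale alone would leave this conflict in place.

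The cost is a wording change to the protocol and the adverse-event form. A few coincidental late local events may be rated possibly related, so the safety profile may look slightly less favourable. The sponsor should also say how to rate an event whose timing is implausible and for which no other cause is known, for example one with onset before the first treatment, because the reworded categories would otherwise leave it without a place.
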